1.2.1 Nonclinical Studies with Cantharidin

Preclinical published data for cantharidin focuses primarily on its effect on epithelial cells, endothelial cells, various carcinoma cells, and myocardial cells. Data most germane to the current study are those examining the effect of cantharidin on epidermal cells, since it is absorbed through the lipid layer of the skin, inducing acantholysis and desmosome disruption of the epidermal cell layer leading to small blisters.

Cantharidin has shown potent in vitro chemotherapeutic activity against a number of human cancer cell types including human bladder cancer T24 cells^[6] and human bladder cancer TSGH 8301 cells.^[7] Pharmacodynamic drug-drug interaction studies of topical application of cantharidin on rat ears showed a decreased anti-inflammatory response from dexamethasone, hydrocortisone, and prednisolone.^[8]

Previously, safety pharmacology studies have been conducted primarily following oral administration, rather than dermally, due to the limited anticipated systemic exposure following topical administration. One study, however, focused on cardiovascular and renal effects of ingested cantharidin in rats. This study showed that cantharidin did not affect heart rate for the experimental period of 24 hours but decreased urine volume.^[9] In a rabbit study, intermediate (1.3 or 1.5 mg/kg) and high (1.9 mg/kg) doses of intravenous bolus injection of cantharidin led to cardiac arrest, but no effects were noted at lower doses (0.6 or 1.1 mg/kg).^[10]

In vitro studies of cantharidin produced positive inotropic responses in guinea pig papillary muscle,^[11] human myocardial tissue,^[12, 13] and bovine coronary artery rings.^[13] Cantharidin inhibits mobilization of synaptic vesicles and depresses calcium release from the sarcoplasmic reticulum, affecting motor function^[14] and causing contraction of bovine smooth muscle.^[15] In GLP-compliant genotoxicity studies, cantharidin could not be evaluated in the chromosomal aberration assay with human peripheral blood lymphocytes, and therefore no conclusions can be made about its clastogenic potential. Cantharidin was negative in GLP-compliant bacterial reverse mutation assays and does not possess mutagenic potential.

1.2.2 Clinical Studies with Cantharidin

Cantharidin has been used by healthcare providers for decades to treat molluscum. The following summarizes significant studies documenting safety and efficacy of this treatment modality.

An ongoing bridging study has been implemented under Investigator IND 114032 to confirm if VP-102 is similar in safety and efficacy to a 0.7% cantharidin compounded formulation of cantharidin studied previously. As of 1 April 2017, VP-102 appears to be safe and well tolerated. There were no treatment related adverse events reported during application to over 1,000 molluscum lesions in 14 subjects with a 6-hour exposure. In an ongoing second part of this study, there have been no treatment related

adverse events reported with application to nearly 250 lesions in 12 subjects with an overnight exposure. The ability of VP-102 to completely clear molluscum is not significantly different from a 0.7% cantharidin compounded formulation, and both the compounded and VP-102 perform significantly better than the best estimate of placebo. Thus, this bridging study is deemed to have met its primary objective in demonstrating that VP-102 appears to be safe and effective in the treatment of pediatric molluscum (IND 114032; NCT# 03017846).

Schainer et al.^[16] published an interim analysis of a two phase, double-blind, placebo-controlled study with the first 52 subjects (2 to 17 years old) who were randomly assigned to receive two treatments with topical 0.7% w/v cantharidin or placebo (with and without occlusion) 3 weeks apart with lesion counts and adverse events assessed every 3 weeks. Most recently, Garelik et al. ([unpublished manuscript](#); with the full analysis of the population treated in Schainer et al.) published the complete results of the Schainer study. Cantharidin or placebo vehicle was administered in a blinded manner at week 0 and week 3 to 94 subjects with a maximum of 50 lesions. At 6 weeks (2 applications spaced 3 weeks apart), a greater percentage of subjects achieved complete lesion clearance in the cantharidin versus placebo arms ($p < 0.05$). Subjects who did not have clearance at week 6 were crossed over to treatment with open-label cantharidin every 3 weeks until all lesions were resolved. In this 94-subject study, 78.4% of the participants achieved total lesion clearance in a median of three visits (range 2 to 9 visits). In the open label group, the median time to clearance was 9 weeks (3 additional treatments with cantharidin) with 87.8% of subjects achieving complete resolution. There were no reported treatment related adverse events demonstrating that cantharidin is an effective and safe treatment for molluscum when applied as an in-office treatment.^[16]

In another exploratory double-blind, placebo-controlled study, 29 children, with no upper limit of lesion count, were treated every 10-14 days over a 2-month period for a maximum of 5 visits.^[17] Only 1-2 lesions were treated on the first visit and up to 20 lesions were treated on subsequent visits. By visit 5, the median lesion count for the cantharidin group was 8 (a reduction of 41% from baseline) whereas the median count for the placebo group was 18 (a reduction of 8% from baseline). Complete clearance of lesions was seen in 15% (2 of 13) of cantharidin-treated subjects and 9% (1 of 16) of the placebo group.

Lastly, a prospective, four-arm, open-label, randomized study investigated the efficacy of four recognized treatments for molluscum (curettage, 0.7% cantharidin, salicylic acid and lactic acid, imiquimod).^[18] For each subject in the cantharidin treatment group, 10 lesions were selectively treated, and the remaining lesions were removed by curettage. Efficacy was based on the number of visits needed for clearance, incidence of side effects, and parental and subject satisfaction. Following curettage, cantharidin had the best tolerability and efficacy profile in this single center study where the investigators were primarily experienced with curettage as the primary treatment modality. Adverse events (AEs) reported in these studies were limited to blistering and pain at the application site. Less frequently, redness, pruritus, and pigment changes have been reported with cantharidin use.

Results of prospective studies are supported by retrospective reports of treatment of molluscum with cantharidin. In a retrospective study of 62 cases of pediatric molluscum involving facial lesions, treatment with cantharidin resulted in the following incidence of side effects; 18% discoloration, 10% blistering greater than expected, and 10% pain. Pruritus, scarring, irritation, bleeding, and spreading of lesions were uncommonly cited. A satisfaction survey of parents following treatment found an average score of 8.7 out of 10. The authors concluded that cantharidin is a safe and effective first-line treatment for molluscum lesions on the face.^[19]

Moye, et al.^[20] performed a retrospective analysis of 405 molluscum subjects (aged 5 months to 20 years old) treated with 0.7% w/v cantharidin. The study involved 1,056 treatments to over 9,688 lesions with an average of 2.6 visits per patient. A parent satisfaction assessment found that 86% of parents were satisfied with the cantharidin treatment or would opt to use it again, while 1.2% of parents were dissatisfied, citing irritation and pain as the reasons. Less than 1% of parents preferred another therapeutic option. The most common AEs in the population were blistering (11%), pain at the treatment site(s) (7%), and severe blistering (2.5%). Less than 1% of patients experienced pruritus, possible mild infection, significant irritation, non-severe pain after treatment, and bleeding.

Cathcart, et al.^[21] also reported on parental satisfaction, efficacy, and AEs in 54 children (aged 3 months to 13 years old) with molluscum after treatment with cantharidin. Parents reported 96% improvement post-treatment with a 78% satisfaction rating. Overall, 46% of patients experienced AEs, including pain, pruritus, secondary

infection, and temporary hypopigmentation while 9% experienced severe pain. The authors concluded that cantharidin “should be considered a potential frontline treatment” for molluscum.

Silverberg, et al.^[22] conducted a retrospective study to determine the safety, efficacy and parental satisfaction in 300 children (mean aged 4.7 years old) with molluscum after treatment with 0.7% w/v cantharidin. 90% of patients experienced complete clearing, 8% experienced significant improvement and 2% reported that the therapy was ineffective. 92% of patients had blistering, 37% experienced erythema (which lasted up to 3 weeks), 14% had mild to moderate pain, and 8% had a change in pigmentation at the site of application. Importantly, no major side effects or secondary bacterial infections were noted. 95% of parents stated that they would proceed with cantharidin therapy again if necessary.

The above studies provide evidence of the safety, efficacy, and widespread use of 0.7% w/v cantharidin topical solution in the treatment of molluscum in children of all ages, with no serious adverse events reported. However, there is a wide variation in the quality of the research conducted, timing between applications, duration of exposure of lesions to cantharidin and the exact formulations of cantharidin used.

1.3 STUDY RATIONALE

For many dermatologists, 0.7% w/v cantharidin has been the treatment of choice for molluscum for decades. However, cantharidin remains an unapproved drug, and there is no reliable or controlled source on the market. This study will evaluate VP-102, a controlled, highly-pure, standardized form of topical cantharidin manufactured under good manufacturing practices in order to address the problems associated with currently available compounded cantharidin products and the needs of patients and medical professionals.

On average, it takes over 13 months to naturally clear molluscum lesions. Unfortunately, one in four children with diagnosed molluscum experience persistent lesions even after 18 months. Subjects with more than 10 molluscum lesions experience a significant negative effect on their quality of life.^[3]

The primary objective of this study is to determine the presence or absence of systemic cantharidin following VP-102 application. Plasma will be evaluated by a

GLP-compliant third party vendor for the presence of cantharidin using a validated GC/MS analytical method (MET012. v1). The unit of analysis is ng/ml with a limit of detection of 1ng/ml in plasma.

The secondary objectives will be to evaluate the safety, efficacy and impact on quality of life with dermal application of VP-102, when applied once every 21 days for up to 4 applications in subjects age 2 years or older. Safety of the treatment will be evaluated by assessing AEs, LSRs, physical examinations, and concomitant medications throughout the study (up until EOS; ~Day 84) compared to baseline. For patients that have completely cleared prior to EOS (~Day 84), all corresponding study related activities will be conducted and an EOS form will be completed.

1.4 DOSE RATIONALE

A 0.7% w/v cantharidin solution is the recognized therapeutic dose of cantharidin for molluscum treatment in dermatological clinical practice^[17, 19-23]. A lower dose of 0.5% was found to be ineffective in the treatment of molluscum.^[24] The 0.7% w/v dose was determined to be safe and effective in a recent double-blind Phase 2 study of 94 subjects for the treatment of childhood molluscum,^[16] Garelik et al. (*unpublished manuscript*) and in an ongoing study of VP-102 (NCT# 03017846) with 26 patients treated as of 1 April 2017.

The anticipated VP-102 label will focus on treatment of patients with any number of molluscum lesions. Each lesion is typically about 1 mm to 4 mm (0.78 mm² to 12.56 mm²) in diameter and Verrica estimates that approximately 5-10 µL of VP-102 is sufficient to cover each lesion. A single use applicator should be sufficient to treat up to approximately 50 molluscum lesions and up to 2 applicators may be used per treatment.

OBJECTIVES

1.5 PRIMARY OBJECTIVE

The primary objective of the study is to determine the presence or absence of systemic cantharidin exposure from a single 24-hour dermal application of VP-102 topical film-forming solution [0.7% (w/v) cantharidin] (VP-102) when applied to molluscum contagiosum (molluscum) lesions on pediatric subjects 2 years old and older.

1.6 SECONDARY OBJECTIVES

The secondary objectives are as follows:

- to assess the safety of VP-102, when applied once every 21 days for up to 4 applications, to treated molluscum lesions on subjects 2 years old and older by assessing adverse events, local skin reactions, physical examinations, and concomitant medications throughout the study compared to baseline.
- to assess the efficacy of VP-102 in the treatment of molluscum lesions as assessed by clearance or reduction of treated molluscum lesions compared to baseline.
- to assess the impact of VP-102 treatment on quality of life of patients as assessed via the administration of the Children's Dermatology Life Quality Index (CDLQI).

2.0 STUDY DESIGN

2.1 BASIC DESIGN CHARACTERISTICS

This is a Phase 2, study that will be conducted in the United States to determine the systemic exposure, efficacy, safety and impact on quality of life of VP-102 (0.7% cantharidin) following treatment of molluscum lesions for up to 4 treatments, 21 days apart, with VP-102 in up to 40 pediatric subjects (2 years or older). Duration of molluscum lesions prior to Day 1 will be recorded but will not be an inclusion/exclusion requirement.

Study drug, VP-102, will be supplied in single-use applicators, with one applicator sufficient to treat at least 50 molluscum lesions. If required due to the number and size of lesions, a second single-use applicator may be used. No more than 2 applicators will

be permitted per subject per treatment. The film-forming Study drug solution will be applied and left on the lesions for approximately 24 hours before the subject and/or parents/guardian washes the lesions with soap and warm water. Those in the Exposure group will remove the dried film after the 24-hour blood draw is obtained. Treatment may be removed prior to the 24-hour timepoint in the event significant blistering, significant pain or treatment emergent AEs are experienced.

Molluscum lesions will be treated without occlusion in all anatomic areas including the face, trunk, back, arms, legs, hands, feet, genital region and buttocks as long as the physician feels it is safe to do so. Subjects participating in the Exposure group must have at least 21 lesions treated at Day 1 treatment to qualify.

The study duration from Day 1 through the EOS visit is up to 12 weeks. Pre-study screening for eligibility (informed consent, inclusion/exclusion criteria and medical history) will occur up to 14 days before, or on Day 1/Study drug administration. Subjects will be treated with application to molluscum lesions every 21 days (\pm 4 days) for a maximum of 4 treatment sessions. Subjects that completely clear prior to ~Day 84 will complete their EOS visit on that day. In the event of scheduling conflicts in subsequent visits after the Day 1 treatment, subjects may be scheduled on 21 ± 4 days following their previous treatment. The next study visit should then be scheduled 21 days after the previous treatment.

Assessment of local skin reactions (LSR) will be performed by the investigator or trained member of the research team at each treatment visit and the EOS visit. LSRs are not considered AEs and are part of the normal and necessary response to treatment. The following clinical responses will be recorded: erythema (including associated swelling), flaking/scaling, dryness and scabbing/crusting during resolution). A Skin Quality Assessment will also be performed as part of the LSR and will assess pigmentation changes (hyperpigmentation or hypopigmentation) and degree of scarring, if applicable.

Parent/subject quality of life and measure of impact of skin disease will be assessed with the CDLQI prior to application of Study drug at each treatment session and at EOS visit. Subjects will also complete a Safety Monitoring Questionnaire at visits 2-5.

Subjects will be given a 24-hour phone number to call the investigator or a clinical research team member in the event of questions or AEs. Evaluations will also be provided by the subject or parent/guardian using the Patient Evaluation of Response to Investigational Treatment (PERIT) form the following day after Study drug application. Parents will also be asked to take and send photos via text or e-mail to the study team for assessment during the 24-hour follow-up call. All observed AEs, local skin reactions and parent-reported AEs will be recorded.

Parents or guardians must provide informed consent, and pediatric subjects older than 5 years must provide assent as required by the IRB before any study procedures are conducted. Subjects must meet all study eligibility criteria through a complete review of pertinent medical history, a symptom/sign evaluation, and limited physical examination. Full inclusion/exclusion criteria are provided in [Section 2.2](#).

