Test product, dose, and mode of administration: Study drug (VP-102) is contained within a single-use applicator. Topical administration results in approximately 5 to 10 μ L of Study drug per molluscum lesion (approximately 1mm to 4mm in diameter). The VP-102 single-use applicator contains 450 μ l (3.15 mg) of 0.7% w/v cantharidin. Up to 2 applicators may be used per patient, but a second applicator may only be necessary if treating >50 lesions.

STUDY SYNOPSIS (continued)

Name of sponsor company: Verrica Pharmaceuticals, Inc.
Name of finished product: VP-102 (0.7% w/v cantharidin delivered via a single-use applicator)
Name(s) of active ingredient(s): Cantharidin
Duration of treatment: The length of study participation from treatment Day 1 is up to approximately 84 days (12 weeks): Up to 4 applications of Study drug at approximately 21-day intervals, followed by a EOS visit approximately 21-days after the final treatment. Subjects are instructed to gently wash all treated lesions with soap and warm water the morning following application (24 hours after treatment or earlier if significant pain or significant blistering has occurred). If not inconvenient, the patient will target a 24-hour removal time point. Washing of intact blisters should be gentle and without use of a washcloth. Washing in a bath or shower is encouraged.
Criteria for evaluation The primary objective of the exposure protocol group is to determine the presence or absence of systemic cantharidin. Due to sample size, power calculations will not be performed. Data will be summarized using descriptive statistics (sample size, mean, median, standard deviation, minimum, maximum) for continuous variables and frequencies and percentages for discrete variables. Corresponding by-subject data listings will be tabulated.
Efficacy: All subjects who meet the screening eligibility criteria for the study and enrolled in the study, will be evaluated for efficacy. Clinical response to treatment of molluscum lesions will be evaluated at each scheduled visit until EOS by counting all molluscum lesions. New or additional treated and untreated lesions will also be counted. LSR will be assessed at each study visit and the EOS visit by the Investigator or trained personnel with a protocol specific LSR form.

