Safety: All subjects who meet the screening eligibility criteria for the study and receive at least one application of Study drug will be evaluated for safety. The following safety parameters will be assessed: 
• Incidence of adverse events (AEs) throughout the study:
○ A subject-by-subject treatment-emergent AE (TEAE) data listing, including verbatim term, preferred term, treatment, severity, and relationship to the Study drug, will be provided.○ The number of subjects experiencing AEs and number of AEs will be summarized by treatment using frequency counts.○ AEs will not include expected local skin reactions such as: minor pain, small blisters, pruritus, erythema, and post-inflammatory pigment changes.○ Reactions to drug administration will be considered an AE if:
▪ Individual blisters develop that are greater than 20mm in diameter. An aggregated blister composed of a number of smaller blisters is not considered an AE.▪ Any medical intervention excluding administration of mild over-the-counter (OTC) pain relievers is required.▪ The event results in discontinuation from the study.

STUDY SYNOPSIS (continued)

Name of sponsor company: Verrica Pharmaceuticals, Inc.
Name of finished product: VP-102 (0.7% w/v cantharidin delivered via a single-use applicator)
Name(s) of active ingredient(s): Cantharidin

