- a. Screening can occur up to 14 days prior to Study drug application on Day 1. Screening can occur on the same day as treatment Day 1/Study drug application. An IRB-approved ICF must be signed before any study specific procedures are performed.
- b. Subjects may be scheduled 21+/- 4 days after treatment in the event of scheduling conflict. If possible the next treatment or study visit should be scheduled 21 days from the day of the subject's last study visit. The 24 hour follow-up may be conducted at +/- 3 hours. Study medication should be removed after the 24 hour draw is completed.
- c. At end of the study (EOS, ~Day 84), all subjects with unresolved molluscum lesions or unresolved treatment-emergent AEs, will be treated by the investigator per local standard of care. Patients who clear all lesions at study visits prior to ~Day 84 will complete all study related assessments that were required at the EOS visit and will not need to return for further assessment. A study completion form will be completed on the day they are cleared.
- d. Confirmation of eligibility criteria.
- e. Demographics: date of birth, sex, race/ethnicity will be collected.
- f. Vital signs (e.g., temperature & heart rate) will be obtained at screening and at each treatment prior to application of Study drug.
- g. Limited physical examination. Symptom- or AE-directed physical examination may be performed if warranted. (See Source/CRF for further outline of assessment.)
- h. Regional lesion counts (head/neck, trunk, upper/lower extremities) should be performed.
- i. LSR assessment will be performed by the Investigator or trained personnel with a protocol-specific LSR form at each treatment visit and the EOS visit.
- j. CDLQI assessment to be completed prior to Study drug application and at EOS visit. CDLQI must be repeated if the first treatment is not completed within 7 days.
- k. To be performed prior to Study drug application and at EOS in any females of childbearing potential (females that are capable of menstruating).

- l. Photography of molluscum lesions will occur at selected clinical sites only.
- m. Study drug may be gently removed from individual lesions prior to 16 hours of application in the event of significant blistering, significant pain or treatment emergent AEs. Study drug should not be removed from the remaining unproblematic lesions until the 24 hour time point is reached. Every effort should be made to complete the PERIT at 24 hours after application.

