4.2.2 Evaluations (Treatment Day 1)

Subjects will return to the clinical site for screening if it was not completed previously, and the following evaluations will be performed:

1. Confirmation of eligibility.
2. Medical history to assess any changes since screening (as described in [Section 4.2.1](#)).
3. Review and recording of any concomitant medications and non-pharmacologic treatments or procedures in the last 14 Days prior to enrollment and since the last study visit.
4. Vital signs (heart rate and temperature).
5. Limited physical examination.
6. Dermatologic exam (as described in [Section 4.2.1](#)).
7. CDLQI assessment.
8. LSR assessment.

9. Urine pregnancy test for females of child bearing potential, defined as capable of menstruating, to determine protocol eligibility.
10. Photographs taken before application of the Study drug (at selected sites only).
11. Application of Study drug.
12. Review and record any AEs and concomitant medications.
13. Completion of PERIT assessment by parent or guardian approximately 24 hours following application of the Study drug.
14. Depending on age of subject, subject or parent/guardian will wash off the Study drug 24 hours post application of Study drug or when convenient after the 24 hour time point is reached provided there are no adverse reactions. Patients/guardians may gently remove the Study drug from lesions without the use of a washcloth in problematic areas prior to the expected 24 hours if the lesions have already blistered or if the patient is experiencing unmanageable pain. Study drug should not be removed from the additional lesions, where possible, until the expected blistering occurs or the 24 hour time point is reached, whichever comes first.
15. A follow-up phone call from the investigator or a designated member of the clinical research team will be conducted the following day after each treatment to allow parents/guardians to ask questions and report any concerns, confirm removal of Study drug, and review the completion of the PERIT assessment.

4.2.3 Evaluations: (Treatments Day 21, 42 and 63):

1. Review and recording of any concomitant medications and non-pharmacologic treatments/procedures since previous visit.
2. Review and recording of any AEs (before and after Study drug application).
3. Vital signs (heart rate and temperature) before Study drug application.
4. Dermatologic exam (as described in [Section 4.2.1](#)) with counting of molluscum lesions.
5. CDLQI assessment.

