2.2.2. Secondary Objectives

The secondary objectives of this study are:

- to assess the safety of VP-102, when applied once every 21 days for up to 4 applications, to treated molluscum lesions on subjects 2 years old and older by assessing adverse events including expected local skin reactions, physical examinations and concomitant medications throughout the study compared to baseline.
- To assess the efficacy of VP-102 in the treatment of molluscum lesions as assessed by clearance or reduction of treated molluscum lesions as compared to baseline.

- To assess the impact of VP-102 treatment on quality of life of subjects as assessed via the administration of the Children's Dermatology Life Quality Index (CDLQI).

3. Study Design

This is a Phase 2 study that will be conducted in the United States to determine the systemic exposure, efficacy, safety and impact on quality of life of VP-102 (0.7% cantharidin) following treatment of molluscum lesions for up to 4 treatments, 21 days apart, with VP-102 in up to 40 subjects (2 years or older). Subjects to be included in the Exposure group must have at least 21 lesions treated at Day 1 to qualify. The Standard treatment group will consist of subjects with fewer than 21 lesions treated at Day 1. Duration of molluscum lesions prior to Day 1 will be recorded but will not be an inclusion/exclusion requirement.

Study drug, VP-102, will be supplied in single-use applicators, with one applicator sufficient to treat at least 50 molluscum lesions. If required due to the number and size of lesions, a second single-use applicator may be used. No more than 2 applicators will be permitted per subject per treatment. In the Exposure group, blood samples for systemic exposure evaluation will be collected on Day 1, prior to the Study drug application (T=0), and 2 (\pm 30 minutes), 6 (\pm 1 hour) and 24 (\pm 3 hours) hours post-application. The film-forming Study drug solution will be applied and left on the lesions for approximately 24 hours before the subject and/or parent/guardian washes the dried film off the lesions with soap and warm water. For those subjects in the Exposure group, the dried film will be removed after the 24-hour blood draw is obtained. Study drug treatment may be removed prior to the 24-hour time point in the event significant blistering, uncontrollable pain or treatment emergent AEs are experienced.

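### On Day 1 the removal rules conflict for the Exposure group, and neither the time of early film removal nor the lesions uncovered is required or shown beside the plasma results

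*Protocol*

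**What the plan says.** **The condition under study.** Protocol 1.5 defines the primary objective as "systemic cantharidin exposure from a single 24-hour dermal application of VP-102". Protocol 2.1 and SAP section 3 have the Exposure group remove the dried film once the 24-hour sample is taken. Schedule footnote b agrees: "Study medication should be removed after the 24 hour draw is completed".

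**Permitted early removal.** Protocol 2.1: "Treatment may be removed prior to the 24-hour timepoint in the event significant blistering, significant pain or treatment emergent AEs are experienced". Footnote m allows it lesion by lesion: "Study drug may be gently removed from individual lesions prior to 16 hours of application in the event of significant blistering". Footnote m and section 4.1 both keep film on the remaining lesions to 24 hours. SAP section 3 has a similar exception with a different pain threshold: "Study drug treatment may be removed prior to the 24-hour time point in the event significant blistering, uncontrollable pain". None of these exempts the Exposure group.

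**The Day 1 instruction.** Protocol 4.2.2 item 14 lets families wash problem areas that have already blistered or are unmanageably painful. It asks that film stay on the other lesions, where possible, only "until the expected blistering occurs or the 24 hour time point is reached, whichever comes first". The synopsis lists small blisters as an expected reaction: "AEs will not include expected local skin reactions such as: minor pain, small blisters".

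**What is recorded and analysed.** The next-day call confirms that the film was removed. PERIT and the LSR form grade the skin's reaction. SAP 11.1 counts lesions treated. SAP section 6 admits a subject to the Exposure population on four completed draws. SAP section 8 summarises results above and below 1 ng/ml, overall and by time point, and lists them.

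**The concern.** The trial is meant to say whether a 24-hour application gives detectable cantharidin. A child whose film came off some or all lesions before the last draw received less than that. On the one day that matters for the primary endpoint, a site has two instructions. One holds the remaining lesions to 24 hours, and the other releases them at ordinary blistering. A site following item 14 would not see itself as departing from protocol.

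If this happens, the 24-hour row combines children with full wear and children with partial wear, and nothing the documents require shows how many of each or how much film was lost. A reader who sees no detections at 24 hours could not say how many children that result describes under the stated condition.

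**Working it through.** **1. The plan's own figure.** The only sample-size figure is the enrolment ceiling: 16 Exposure completers + 16 standard + 8 replacements = 40, as protocol 2.2 states. There is no power or precision figure to reproduce.

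**2. The removal rules side by side, Exposure group, Day 1.**

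| Source | Trigger for early removal | Remaining lesions |
|---|---|---|
| Protocol 2.1 | significant blistering, significant pain, TEAE | Exposure film off after the 24 h draw |
| Footnotes b, m; section 4.1 | same triggers (m, 4.1) | kept to 24 h (m, 4.1); removed after the draw (b) |
| SAP 3 | significant blistering, uncontrollable pain, TEAE | Exposure film off after the 24 h draw |
| Protocol 4.2.2 item 14 | already blistered, or unmanageable pain | kept, where possible, until expected blistering or 24 h, whichever is earlier |

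Only item 14 releases the non-problem lesions on a normal drug effect.

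**3. Where early removal could appear in the data.**
- Next-day call (4.2.2 item 15): confirms removal; no time or lesion count requested.
- PERIT (SAP 11.4) and LSR form (SAP 11.3): severity of reaction, not wear.
- Extent of exposure (SAP 11.1): lesions reported minus lesions not treated, so it is fixed at application.
- AE records (protocol 2.3.1): include action taken. SAP 3 and 11.3 record LSRs as AEs, so some removals may be visible here.
- Deviations (SAP 7.2): all are listed by subject, so removal against 2.1 may be visible here.
- CRF: not supplied. Protocol 7.2.1 and SAP 5 would put any removal field in a by-subject listing.

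None of these requires a clock time or a number of lesions.

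**4. Size across children (illustration).** Assume no detections. The two-sided exact upper 95% limit for n full-wear children is 1 − 0.025^(1/n). The documents give no early-removal rate, so the number of early removers is assumed.

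| Early removers of 16 | n with full wear | Upper limit |
|---|---|---|
| 0 | 16 | 20.6% |
| 1 | 15 | 21.8% |
| 2 | 14 | 23.2% |
| 4 | 12 | 26.5% |
| 8 | 8 | 36.9% |

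For orientation, protocol 1.2.2 reports severe blistering in 2.5%, severe pain in 9%, and blistering beyond expectation in 10% in separate series of children treated with cantharidin. Applied to 16 children, 16 × 0.025 = 0.4 and 16 × 0.10 = 1.6, so about 0 to 2. Any blistering ranged from 11% to 92%: 16 × 0.11 = 1.8 and 16 × 0.92 = 14.7. These are reaction rates, not removal rates, and preparations and wear times differed.

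**5. Size within a child (illustration).** If k of 21 lesions (the Exposure minimum) are washed at hour t, the share of planned lesion-hours kept is 1 − (k/21)(1 − t/24).
- k = 1, t = 12: 1 − 0.0476 × 0.5 = 97.6%.
- k = 21, t = 12: 1 − 1 × 0.5 = 50.0%.

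This measures wear, not absorption; no document says absorption is proportional to wear time.

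**The case against.** The best case for the plan has four parts.

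- **The endpoint does not demand full wear.** Protocol 2.3 asks for presence or absence of exposure after treatment in patients with 21 or more lesions. Safety removal is part of the regimen, so analysing all completers as treated is legitimate. This stands, and the planned all-subject row should remain. But the objective in 1.5 and in the SAP names a 24-hour application, so the reader needs to know who had one.
- **Some capture exists.** A reader might infer that early removal would be invisible. The documents do not support that: AE action-taken entries, the deviation listing and any CRF field, which would be listed, could identify affected children. What remains is that no time or lesion count is required and none is set beside the plasma results.
- **The specific rule governs.** A reader might take the synopsis wording, "If not inconvenient, the patient will target a 24-hour removal time point", as releasing Exposure subjects from 24 hours. It is general text for all subjects, and the Exposure rule overrides it. That argument does not rescue item 14, which is itself the Day 1 instruction.
- **The numbers are small.** With the significant-reaction trigger, one or two children is a plausible guide, and the limit barely moves. This stands. The 4-of-16 and 8-of-16 rows have no direct support and matter only if item 14 is followed literally.

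**Conclusion.** The point holds as a conflict in the Day 1 instructions together with a gap in what must be recorded and shown. It is modest. If removal is confined to a few problem lesions in one or two children, the upper limit for full wear rises from 20.6% to 21.8–23.2%, and each child keeps most of the planned wear. It grows only if sites act on item 14's blistering clause, and the required data cannot show which happened.

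A reader might infer that a negative 24-hour result would be biased towards no exposure. The documents do not support a direction: shorter wear could lower the level, while more damaged skin could raise absorption. Nor is the whole primary result in doubt. The 2-hour and 6-hour samples are affected only by removal before them, and SAP section 8 takes any value above 1 ng/ml as presence.

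The conclusion rests on assumed numbers of early removers, an assumed zero detections, and the absence of any visible requirement for removal time or lesion count. The CRF was not available and may hold such a field.

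**What to change.** 1. In protocol 4.2.2 item 14, for Exposure subjects on Day 1, match section 2.1: early removal only for significant blistering, significant pain or a TEAE, on the problem lesions, with the rest kept until after the 24-hour draw. Safety removal stays allowed.
2. At the existing 24-hour Exposure visit (footnote o), record the clock time of any earlier removal and the number of lesions uncovered.
3. In SAP section 8, list both beside each subject's plasma results. Keep the all-subject 24-hour row as planned. Add one supportive descriptive row for subjects with no early removal, labelled as selected on a post-treatment event.

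The cost is one wording change, one line on a form for a visit that already takes place, two listing columns and one table row. The added row has a smaller denominator and leaves out children who reacted, so it must not replace the planned row.
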